19.2.2 Safety Variables

Laboratory Tests and ECG

Assessments of laboratory tests and ECGs at unscheduled visits and withdrawal visits will be assigned to a nominal visit in the Placebo-controlled Period according to the visit windowing specified in Panel 10 for patients in the APTS. Assessments for patients not receiving any infusions of IMP will be assigned to Visit 2 (Baseline). For patients receiving an infusion of

IMP in the Extension Period, assessments of laboratory tests and ECGs at unscheduled visits and withdrawal visits will be assigned to a nominal visit in the Extension Period according to the visit windowing specified in Panel 11.

Panel 10 Visit Windows for Placebo-Controlled Period – Laboratory tests, ECG

Nominal Visit Number	Nominal Visit Week	Nominal Visit Day	Time Window
V1 (Screening Visit)	-4	-28	NA
V2 (Baseline Visit)	0	0	NA
V5	12	84	After start of first IMP infusion to day 126
V8	24	168	Day 127 to start of Visit 8 IMP infusion

Panel 11 Visit Windows for Extension Period – Laboratory tests, ECG

Nominal Visit Number	Nominal Visit Week	Nominal Visit Day	Nominal Visit Day Relative to Visit 8 IMP Infusion	Time Window Relative to Visit 8 IMP Infusion
V11	36	252	84	After start of Visit 8 IMP infusion to day 126
V14	48	336	168	Day 127 to day 210
V17	60	420	252	Day 211 to day 294
V20	72	504	336	> 294

Vital signs will be assessed before and after infusion at nominal visits. For unscheduled or withdrawal visit assessments of vital signs, the values will be assigned a nominal visit according to Panel 12 and Panel 13.

Nominal Visit Number	Nominal Visit Week	Nominal Visit Day	Time Window
V1 (Screening Visit)	-4	-28	NA
V2 (Baseline Visit) pre-dose	0	0	NA
V2 (Baseline Visit) post-dose	0	0	After start of first IMP infusion to day 42
V5 pre-dose	12	84	Day 43 to start of V5 IMP infusion
V5 post-dose	12	84	After start of V5 IMP infusion to day 126
V8 pre-dose	24	168	Day 127 to start of Visit 8 IMP infusion

Panel 12 Visit Windows for Placebo-Controlled Period – Vital Signs

Nominal Visit Number	Nominal Visit Week	Nominal Visit Day	Nominal Visit Day Relative to Visit 8 IMP Infusion	Time Window Relative to Visit 8 IMP Infusion
V8 post-dose	24	168	0	After start of V8 IMP infusion to day 42
V11 pre-dose	36	252	84	Day 43 to start of V11 IMP infusion
V11 post-dose	36	252	84	After start of V11 IMP infusion to day 126
V14 pre-dose	48	336	168	Day 127 to start of V14 IMP infusion
V14 post-dose	48	336	168	After start of V14 IMP infusion to day 210
V17 pre-dose	60	420	252	Day 211 to start of V17 IMP infusion
V17 post-dose	60	420	252	After start of V17 IMP infusion to day 294
V20	72	504	336	> 294

If there is more than one assessment at a visit (either due to multiple assessments or because an unscheduled or withdrawal visit assessment is mapped to a nominal visit with an already existing value) the value that will be used in summary tables by visit will be the one closest to the nominal day for the visit but prioritizing values from scheduled visits above values from withdrawal or unscheduled visits. In the ordering of multiple values, assessments without recorded time will come after assessments with recorded time and the first in the ordering will be picked.

19.3 Handling Missing or Incomplete Dates/Times

19.3.1 Missing Headache End Date and Time

If the end date and time for a headache recorded in the eDiary is missing, the headache end date and time will be imputed as follows:

If there exists an entry in the evening eDiary at a date after the date of the start of the headache entered in the headache eDiary, the headache end date and time is imputed with the date and time of the last evening eDiary entry.

If there are no entries in the evening eDiary after the date of the start of the headache entered in the headache eDiary, the headache end date and time is imputed with the start date of the headache and the time 23:59.

Headaches that are not reported as stopped by the patient are missing the answers to the questions that allow for the determination of whether the headache was a migraine or not. Headaches with missing 'end' information will be classified as migraines (and thereby also as headaches).

Note that for each patient, it is only possible to have a missing end date and time for the last headache ever entered, since a patient needs to complete a headache in order to report a new one in the headache eDiary.

19.3.2 Withdrawal Date

Missing withdrawal dates will not be imputed and time to withdrawal from treatment will not be calculated for missing withdrawal dates.

19.3.3 Medical Disorder Start and Stop Dates

Incomplete dates will not be imputed. Classification of events into *concurrent medical disorders* or *past disorders* will be based on the reported ongoing status.

19.3.4 Medication Start and Stop Dates

Imputation of incomplete or partially missing dates will be performed in order to document the assigned categories specified in Section 9.

The algorithm for imputing the start dates will follow the one used for imputing adverse event start dates, see Section 19.3.5.

For imputing stop dates, the following will apply, where UK and UKN indicate unknown or missing day and month, respectively:

- UK-MMM-YYYY: Medication end date is imputed with the last day of the month
- UK-UKN-YYYY: Medication end date is imputed with 31-DEC-YYYY

Medications marked as ongoing are considered concomitant medications in one or both of the periods (Placebo-controlled Period and Extension Period), depending on the (possibly imputed) start date, i.e. if the start date is at or after the date of V8 IMP infusion, the medication is only considered ongoing in the Extension Period.

19.3.5 Adverse Event Start and Stop Dates

Imputation of partially or completely missing dates will be included in data in order to document the classification of the treatment emergent status and assignment of the adverse event to a period. For an adverse event with an imputed start date, the classification of treatment emergent will depend only on whether the imputed date is the same as the date(s) of infusion and not the timepoint of the infusion, since start times for adverse events will not be imputed. No duration will be calculated for adverse events with incomplete start-or-stop dates or for ongoing adverse events.

Imputation will follow the algorithm below. If an imputed start date after this procedure is after the end date, the start date will be set to the end date.

Start Dates

Patients with no IMP infusion

For patients who have not been treated, the imputation of AE start date will be performed as follows, where UK and UKN indicate unknown or missing day and month, respectively:

- UK-MMM-YYYY: The start date will be imputed with either the 1st of the month, or date of Visit 1. Date of Visit 1 will be used if that is the later of the two and if it is within the specified month and year
- UK-UKN-YYYY: The start date will be imputed with either JAN 1, or date of Visit 1. Date of Visit 1 will be used if it is within the specified year

If the AE start date is completely missing, it will be set equal to the date of Visit 1.

Patients who received at least one IMP infusion

For patients, who have been treated, the imputation of AE start dates will be performed as follows:

- UK-MMM-YYYY:
 - If the year and month are equal to the year and month of treatment start date, the adverse event start date is imputed with the date of first dose of IMP
 - If the year is equal to the year of treatment start date: If the month is prior to the treatment start date, the adverse event start date is imputed with the last day of the month. If the month is equal to the month of the treatment start date, see above. If the month is after the month of the treatment start date, the adverse event start date is imputed with the first day of the month

- $\circ~$ If the year is prior to treatment start date, the adverse event start date is imputed with the last day of the month
- If the year is after the year of treatment start date, the adverse event start date is imputed with the first day of the month
- UK-UKN-YYYY:
 - $\circ~$ If the year is equal to the year of treatment start date, the adverse event start date is imputed with treatment start date
 - If the year is prior to the year of treatment start date, the adverse event start date is imputed with 31-DEC-YYYY
 - If the year is after the year of treatment start date, the adverse event start date is imputed with 01-JAN-YYYY

If the AE start date is completely missing, it will be set equal to treatment start date.

End Dates

Missing AE end dates will not be imputed.

Incomplete Intensity Change Dates

If the day is missing in a date of intensity change for an adverse event, the date will be imputed using the same algorithm as described above for incomplete adverse event start dates.

If this results in an imputed start date that is after the end date of the original event or after an intensity change that comes after the intensity change in question, the start date will be imputed with the end date of the original event or the date of the later intensity or change.

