13.1.4 Allocation of TEAEs to Treatment Periods

TEAEs will be allocated to treatment periods according to the time of onset of the adverse event:

- *TEAE in the Placebo-controlled Period* a TEAE that starts before the date and time of the start of Visit 8 IMP infusion
- *TEAE in the Extension Period* a TEAE that starts during or after administration of Visit 8 IMP infusion

For allocation of TEAEs to treatment periods, the same rule for imputed dates as specified above (in Section 13.1.3) applies, i.e. for incomplete start dates, only the imputed start date and not the time (which will not be imputed) of the adverse event will be taken into account in the allocation of the TEAE to periods.

If an adverse event starts on the day of the Visit 8 IMP infusion but with an unknown start time, the adverse event will be classified as treatment-emergent in the Placebo-controlled period.

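### AE start-date imputation ignores the Visit 8 infusion, so Extension events with an unknown day in the Visit 8 month, an unknown month in the Visit 8 year, or no start date at all are allocated to the Placebo-controlled Period

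*SAP*

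**What the plan says.** SAP 19.3.5 gives the imputed start date two jobs. It is made "in order to document the classification of the treatment emergent status and assignment of the adverse event to a period". For treated patients the branches are:

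- Unknown day, month of first dose: "the adverse event start date is imputed with the date of first dose of IMP".
- Unknown day, later month of the first-dose year: "If the month is after the month of the treatment start date, the adverse event start date is imputed with the first day of the" recorded month. Months in later years are treated the same way.
- Unknown day and month, first-dose year: "If the year is equal to the year of treatment start date, the adverse event start date is imputed with treatment start date".
- Unknown day and month, later year: "If the year is after the year of treatment start date, the adverse event start date is imputed with 01-JAN-YYYY".
- Completely missing date: the treatment start date.

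If the imputed start falls after the AE end date, it is moved back to the end date.

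SAP 13.1.4 places a TEAE in the Placebo-controlled Period if it starts before the Visit 8 infusion, and otherwise in the Extension. Where the start is incomplete, "only the imputed start date and not the time (which will not be imputed) of the adverse event will be taken into account in the" assignment. An event on the Visit 8 date with unknown clock time goes to the Placebo-controlled Period.

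Under SAP section 2, patients randomized to placebo start eptinezumab 100 mg or 300 mg at Visit 8. Under SAP 13.1.1, AE tables are by treatment group before Visit 8 and by treatment sequence after it.

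**The concern.** The algorithm has an anchor for its first job (treatment-emergent status) and none for its second, "assignment of the adverse event to a period". Every branch for treated patients looks only at the first dose. Where the known part of the date fits both sides of Visit 8, the imputed date falls on or before Visit 8, whatever the true onset.

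Visit 8 is not merely administrative. For a former placebo patient it is the first eptinezumab infusion. An event that began on active drug is then classed as a placebo TEAE and is missing from the placebo-eptinezumab columns of the Extension TEAE tables. For a patient on eptinezumab throughout, an Extension event moves into the randomized comparison.

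Timing adds a second problem. SAP 2.1 has all Extension output prepared after the clinical study report (CSR) is final. An event first reported after the Placebo-controlled database lock, but imputed to before Visit 8, is too late for the CSR tables and is excluded by its imputed date from the Extension TEAE tables. It may appear in neither.

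**Working it through.** The documents state no figure for this, so there is none to reproduce. The check applies the rules as written.

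**Inputs from the documents.** The imputation branches of SAP 19.3.5; the allocation and tie rule of SAP 13.1.4; period lengths of 24 weeks = 168 days and 48 weeks = 336 days (protocol 3.1).

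**Assumptions, not in the documents.** Visit 8 exactly on day 168; one event on each of Extension days 1 to 336; first doses on each day of one calendar year (2021); no end-date cap. An event counts as misallocated if its imputed date is on or before the Visit 8 date.

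**Worked dates.**

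| First dose | Visit 8 | True onset | Recorded as | Imputed to | Allocated to |
|---|---|---|---|---|---|
| 18 Jan 2021 | 5 Jul 2021 | 20 Jul 2021 | unknown day, Jul 2021 | 1 Jul 2021 | Placebo-controlled (wrong) |
| 18 Jan 2021 | 5 Jul 2021 | 10 Sep 2021 | unknown day, Sep 2021 | 1 Sep 2021 | Extension (right) |
| 18 Jan 2021 | 5 Jul 2021 | 10 Sep 2021 | 2021 only | 18 Jan 2021 | Placebo-controlled (wrong) |
| 1 Nov 2020 | 18 Apr 2021 | Sep 2021 | 2021 only | 1 Jan 2021 | Placebo-controlled (wrong) |

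**Share of Extension events misallocated.** The denominator is 365 first-dose dates × 336 days = 122,640.

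- Unknown day: 5,373 / 122,640 = 4.4% (0 to 8.9% by first-dose date). This is all 5,373 events in the Visit 8 calendar month and 0 of 117,267 in later months.
- Unknown day and month: 66,024 / 122,640 = 53.8% (0 to 100% by first-dose date). This is all 66,024 events in the Visit 8 calendar year and 0 of 56,616 in later years.
- Completely missing: 122,640 / 122,640 = 100%.

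**Other direction.** No Placebo-controlled event is allocated to the Extension in any of the three cases.

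**Sensitivity to the first-dose calendar.** First doses over 480 days from 1 June 2020 give 7,041 / 161,280 = 4.4% for unknown day and 89,423 / 161,280 = 55.4% for year only. First doses from 1 June 2020 to mid-June 2021 (380 days) give 5,478 / 127,680 = 4.3% and 66,594 / 127,680 = 52.2%. The second calendar fits protocol edition 3.0 better, because its change summary, dated 30 November 2021, treats the Placebo-controlled Period as complete.

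**Does anything else repair it?** The end-date cap can only move a start earlier. The exception in SAP 13.1.3 for events the investigator judged to precede the study drug concerns treatment-emergent status at the first dose, not the period.

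**A bare Visit 8 anchor.** Suppose the Visit 8 date were imputed whenever the known part is compatible with it. Misallocation of Extension events falls to 0%, but true Placebo-controlled events pushed into the Extension rise from 0% to 8.8% (unknown day), 76.9% (year only; 71 to 78% over the three calendars) and 100% (fully missing). The remedy therefore needs more information than the date fragment.

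**The case against.** The strongest reply is that very few events are involved. AEs are collected at contacts every 4 weeks, start and stop dates are required, and the data are checked and source-verified (protocol 8.5, 8.6, 10.3, 11.1.1 and chapter 12). Year-only and fully missing dates, where the failure rate is high, should be rare. Where dates are usually nearly complete, the rate is about 4%. AE listings show dates as collected, so partial dates stay visible wherever the event is listed. All of this stands and sets the priority.

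Three stronger readings are tempting, and the documents do not support them.

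- **Every Extension event with an unknown day or month is dated back.** It is not. The first-of-the-month rule is right for every month after the Visit 8 month, and the 1 January rule is right for every year after the Visit 8 year.
- **The placebo AE rate is raised relative to eptinezumab.** The same rule can add events to the Placebo-controlled counts of all three arms. Nothing in the documents fixes the net effect on the comparison.
- **All such events appear in the CSR as placebo TEAEs.** Only events recorded before the Placebo-controlled lock can. Later ones may go untabulated instead.

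It is also fair to say that the SAP already resolves a tie at Visit 8 in favour of the earlier period. That convention covers a known date with an unknown clock time. It does not justify a rule that cannot see Visit 8 when a month, a year or the whole date is in doubt.

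**Conclusion.** The gap is real, one-directional and confined to three cases: unknown day in the Visit 8 month, unknown month in the Visit 8 year, and a fully missing start date. In these cases every Extension event goes to the Placebo-controlled Period. Under even spread of onset and first doses, that is about 4% of Extension events with an unknown day, 52 to 55% with a year only, and 100% with no date.

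These are shares of events with incomplete dates, not of all AEs. The documents do not give the number of incomplete dates, so the absolute count is unknown and probably small. One reading matters at the margin: for an imputed date equal to the Visit 8 date, SAP 13.1.4 points to the on-or-after rule of 13.1.3 but also sends unknown-time events on that day to the earlier period. The working uses the latter.

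This is a minor point of specification. It is worth correcting because it concerns which treatment an AE is attributed to in switchers, and because some events could drop out of both sets of TEAE tables.

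**What to change.** Amend SAP 19.3.5 for patients who received the Visit 8 infusion. When the known part of the start date is compatible with both periods, including a completely missing date:

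1. Keep the present rule if the AE ended before Visit 8, or was first recorded at a visit or phone contact before the Visit 8 infusion.
2. Otherwise allocate the event to the Extension Period, with the Visit 8 date as imputed start.

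Two consequential edits are needed. SAP 13.1.4 should say that its rule for unknown start time on the Visit 8 date does not apply to these imputed events, or it would send them straight back. Events with an imputed start date should be excluded from the day-of-dosing table (SAP 13.1.6) and from the infusion-day criteria for AEs of special interest (Table 6). Otherwise the imputed Visit 8 date would create apparent infusion-day events.

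The cost is a few lines of text and a small amount of programming to use the visit of first report, which is not among the AE details listed in protocol 10.3 and would have to be derived from the data-entry record. The downside is that a few events that began shortly before Visit 8 but were first reported afterwards will count in the Extension.

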19.4 Data with Multiple Records

19.4.1 Dose Changes in Medication

Dose changes in medications are recorded on multiple rows in the dataset, with different start and stop dates. When classifying medications into categories (see Section 9), each dose is considered a separate medication, and the same medication can be assigned to several categories for the same patient. Within a category, multiple entries contribute as a single count.

19.4.2 Changes in Intensity or Seriousness of Adverse Events

An adverse event that changes in intensity in a period will contribute to the count of events as a single event.

In summaries of adverse events presented by intensity, the maximum intensity of the adverse event will be used. The maximum intensity is searched for in events with changes, as well as over repeated events based on the preferred term. Adverse events for which information on intensity is missing will be classified as *severe*.

Adverse events with an update in seriousness will be included in ADaM with only one row. For such an event, the start date of the serious adverse event will be set to the start date of the original event. This means that an adverse event with a start date prior to first infusion of IMP (i.e. not classified as treatment-emergent) that is registered as serious after first IMP infusion will still not be classified as treatment-emergent, unless a change in intensity is taking place after first IMP infusion as well.

Adverse events for which information on seriousness is missing will be classified as serious.

References

- 1. International Headache Society (IHS), Headache Classification Committee. The International Classification of Headache Disorders, 3rd edition 2018 (ICHD-3 2018).
- 2. Robinson LD and Jewell NP. Some surprising results about covariate adjustment in logistic regression models. International Statistical Review. 1991; 59: 227-240.
- 4. Little R and Yau L. Intent-to-treat analysis for longitudinal studies with drop-outs. Biometrics. 1996; 52: 1324-1333.
- 5. Rubin, DB. Multiple imputation for nonresponse in surveys. New York: Wiley; 1997.
- 6. United States Food and Drug Administration (US FDA). Guidance for Industry: Drug-induced liver injury: premarketing clinical evaluation. July 2009.

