13.1.3 Classification of Adverse Events

Adverse events will be classified according to the time of onset of the adverse event:

- *pre-treatment adverse event* an adverse event that starts on or after the date the patient signed the *Informed Consent Form* and prior to the date and time of first dose of IMP
- *treatment-emergent adverse event* (TEAE) an adverse event that starts or increases in intensity during or after administration of the first dose of IMP

For handling of adverse events with incomplete start dates to facilitate this classification, see Section 19.3.5. Note that adverse events with incomplete start dates will be classified as treatment-emergent simply if the imputed start date is on or after the date of first IMP infusion, since the start time of the adverse event will not be imputed, unless the investigator in such a case has assessed that the causality to IMP is "Not Related - Prior to IMP". An adverse event is considered causally related to the use of the IMP when the causality assessment by the investigator is *probable* or *possible*. If the causality assessment is missing, the adverse event is considered causally related.

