13.1.5 Presentation of Adverse Events

A listing of all adverse events starting at or after entering the Extension Period, including a flag for TEAEs will be included in the *addendum to CSR* based on the APTS_LT.

A similar listing of all adverse events occurring before entering the Extension Period will be produced for the *CSR* based on APRS.

For each period, an overview of the numbers and percentages of patients with TEAEs, serious adverse events (SAEs), TEAEs leading to infusion interruption, TEAEs leading to withdrawal, and of patients who died will be provided based on the APTS/APTS_LT. For TEAEs, SAEs, and TEAEs leading to withdrawal, the total number of events will be included.

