13.1.8 Presentation of Serious Adverse Events

All SAEs occurring before entering the Extension Period will be listed for the APRS for inclusion in the *CSR*.

All SAEs occurring at or after entering the Extension Period will be listed for the APTS_LT for inclusion in the *addendum to CSR*.

Treatment-emergent SAEs will be summarized for the Placebo-controlled Period based on APTS and for the Extension Period based on APTS_LT by:

- SOC and preferred term
- preferred term

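### An adverse event that starts in screening and turns serious after the first infusion, at unchanged intensity, is left out of the by-arm treatment-emergent SAE tables

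*SAP*

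**What the plan says.** SAP 13.1.3 defines a treatment-emergent adverse event as "an adverse event that starts or increases in intensity during or after administration of the first dose of IMP", and protocol 16.9.1 defines it the same way. There are two triggers, onset and higher intensity. Becoming serious is not one of them.

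SAP 19.4.2 applies this to events whose seriousness is updated. One row is kept per event, and "the start date of the serious adverse event will be set to the start date of the original event". The section then spells out the result: an event that began before dosing and is "registered as serious after first IMP infusion will still not be classified as treatment-emergent". It allows a single exception, worded as "unless a change in intensity is taking place after first IMP infusion as well".

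In SAP 13.1.8 the tables and the listing differ in scope. For the tables, by system organ class and preferred term and by preferred term alone, "Treatment-emergent SAEs will be summarized for the Placebo-controlled Period based on APTS". For the listing, "All SAEs occurring before entering the Extension Period will be listed for the APRS". The overview in SAP 13.1.5 opens "For each period, an overview of the numbers and percentages of patients with TEAEs, serious adverse events (SAEs". It puts the treatment-emergent label on adverse events, infusion interruptions and withdrawals, but not on SAEs or deaths.

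**The concern.** Adverse events are collected from consent (protocol 10.1.1), and SAP 4.1 gives a screening period of 28-30 days. Some events will start in that window and still be running at the first infusion. If one of them then puts the patient in hospital, its course on treatment has worsened in a way that safety tables exist to show. Under 19.4.2 the worsening counts only if the intensity grade moves too. An event already graded severe is at the top of the scale, so its intensity cannot increase at all.

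The by-arm SAE table is where a reader compares arms. A listing carries the same event but gives no incidence by arm. SAEs are usually few in a trial of this kind, so even one or two misplaced events could be noticed.

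**Working it through.** No arithmetic applies: the point is a classification rule, and the plan states no figure to reproduce. I followed one event, with onset in screening and seriousness after the first infusion, through the sections.

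**Can seriousness change while intensity does not?** Yes. Protocol 10.1.1 rests seriousness on outcomes such as death, threat to life and hospitalisation. Protocol 10.1.2 grades intensity by how far the event interferes with normal activities. The two are assessed separately.

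**Where the event goes:**

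- *Intensity unchanged after first infusion.* Neither trigger in 13.1.3 is met, and 19.4.2 says outright that the event is not treatment-emergent. It is absent from both SAE summaries in 13.1.8. It is also absent from the TEAE summaries in 13.1.6 (including causally related TEAEs), the withdrawal summaries in 13.1.9 and the special-interest summaries in 13.1.11. It is present in the SAE listing.
- *Intensity rises after first infusion.* The event is treatment-emergent and appears in the SAE summaries.
- *Intensity falls after first infusion.* The sections disagree. The exception in 19.4.2 is worded as any change in intensity, while 13.1.3 and protocol 16.9.1 require an increase.

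**Does the 13.1.5 overview count the first case?** It cannot be settled from the text. SAEs are unqualified there, which suggests that all are counted. But the table is produced for each period, the event's start date has been reset to screening, and the only rule for placing events in periods covers TEAEs: "TEAEs will be allocated to treatment periods according to the time of onset of the adverse event". Patients who died are counted without any such condition.

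**Comparison with the SAP's other defaults.** Missing seriousness is taken as serious and missing intensity as severe (19.4.2). Missing causality is taken as related (13.1.3). For a treated patient, a completely missing start date becomes the treatment start date (19.3.5). So an event with no known start is counted as treatment-emergent, while one documented as turning serious after infusion is not. The rule for seriousness updates is less cautious than the defaults around it.

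**Size.** The documents give no rate for SAEs or for screening events that later become serious, so the number affected cannot be derived.

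**The case against.** The case for leaving the rule alone has several sound parts.

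- The rule is explicit, prespecified, identical for all arms and consistent with the protocol's own definition. That stands: it is a weak definition, and the two documents do not contradict each other on it.
- Nothing is hidden. All SAEs are listed for the randomised set, SAEs are reported to the sponsor within 24 hours (protocol 10.4), and a data monitoring committee with unblinded access follows safety. That stands, but none of it gives a reader a by-arm incidence.
- Worsening of a disorder that the patient already had is recorded as an adverse event in its own right (protocol 9.4.1). With onset after dosing it is a TEAE. That stands and narrows the point: the gap covers events that first arose during screening, not pre-existing conditions in general.
- A mild or moderate event that leads to hospital would often change grade, and changes go on an intensity log (protocol 10.3). A severe, ongoing screening event might also keep the patient from being dosed. Both make the case rarer; neither rules it out.
- The data items in protocol 10.3 include no date on which seriousness began, and a registration date is not an onset date. This limits how the fix is built. It does not defeat it: 19.4.2 speaks of setting the SAE start date to the original one, which suggests that a separate date may exist.

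**Conclusion.** The concern holds in a narrow form. As written, SAP 19.4.2 and 13.1.8 together omit from the by-arm treatment-emergent SAE summaries an event that began in screening and became serious on treatment without a change in intensity. That consequence needs no assumption; only its frequency is unknown. Affected events are probably few and could be zero.

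A reader might infer more, and the documents do not support it:

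- *That such an event is visible only in a listing.* The 13.1.5 overview may count it.
- *That a death on treatment could disappear from the by-arm output.* The overview counts deaths whatever the treatment-emergent status.
- *That the rule makes the drug look safer.* It applies alike to every arm. It favours the drug only if the drug aggravates events that began in screening; otherwise it under-counts in all arms.
- *That a set share of SAEs is lost.* One could assume that 2% of 840 patients (0.02 × 840 = 16.8, about 17) have an on-treatment SAE and that one or two of these began in screening, giving 1/17 = 6% or 2/17 = 12%. Both inputs are invented and zero such events is as admissible, so I attach no percentage.

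**What to change.** In SAP 13.1.3 and 19.4.2, classify an event as treatment-emergent and serious when the date on which it met a seriousness criterion is at or after the start of the first infusion, whatever its intensity. Use the date on which seriousness began, not the date it was registered; otherwise an SAE from before dosing that was reported late would be turned into a TEAE.

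If that date is not in the data, keep the present classification. Add a by-arm count of all SAEs with onset before the first infusion and a seriousness update after it, shown beside the 13.1.8 tables.

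In either case:

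- state in 13.1.5 whether the overview counts these events;
- reconcile the any-change wording in 19.4.2 with the increase required by 13.1.3 and protocol 16.9.1;
- if the placebo-controlled data have already been unblinded, label the new output as added afterwards.

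The cost is SAP wording and one extra derivation or one small table. Treatment-emergent SAE counts may rise slightly in any arm.
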